Modelling repurposed from pandemic influenza is currently informing all strategies for SARS-CoV-2 and the disease COVID-19. A customized disease specific understanding will be important to understand subsequent disease waves, vaccine development and therapeutics. For this reason, ISARIC (the International Severe Acute Respiratory and Emerging Infection Consortium) was set up in advance. This focuses on hospitalised and convalescent serum samples to understand severe illness and associated immune response.

However, many subjects are seroconverting with mild or even subclinical disease. Information is needed about subclinical infection, the significance of baseline immune status and the earliest immune changes that may occur in mild disease to compare with those of SARS-CoV-2. There is also a need to understand the vulnerability and response to COVID-19 of the NHS workforce of healthcare workers (HCWs). HCWs present a cohort with likely higher exposure and seroconversion rates than the general population, but who can be followed up with potential for serial testing enabling an insight into early disease and markers of risk for disease severity.

We have set up “**COVID-19: Healthcare worker Bioresource: Immune Protection and Pathogenesis in SARS-CoV-2**” (Figure 1). This urgent fieldwork aims to secure significant (n=1000) sampling of healthcare workers (demographics, swabs, blood sampling) at baseline, and weekly whilst they are well and attending work, with acute sampling (if hospitalised, via ISARIC, if their admission hospital is part of the ISARIC network) and convalescent samples post illness. We will also collect samples at 6 and 12 months from baseline to assess for persistence/ decay of immune protection. These will be used to address specific questions around the impact of baseline immune function, the earliest immune responses to infection, and the biology of those who get non-hospitalized disease for local research and as a national resource. A subset of participants will be invited to undertake in depth analysis of specific subsets of circulating immune cells that contribute to the immune response to the virus.

The proposal links directly with other ongoing ISARIC and community COVID projects sampling in children and the older age population.

Figure 1. Study design

Version 1.4 21/09/2020

2. Aims and Objectives

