- To swiftly create the bioresource to understand baseline host factors and early responses that determine protection and pathogenesis in SARS-CoV-2 infection across NHS HCWs.
- to assess genetic influences on disease severity following infection with COVID-19 infection

Hypothesis

- Baseline immune status and early immune responses during subclinical phase of infection and including the pauci-symptomatic and seroconverters will mechanistically determine clinical outcomes in NHS HCWs.

Primary objective

Identify baseline and early immune responses that predict incident disease stratified by time interval to disease in NHS HCWs.

Secondary objectives

Identify immune responses that predict seroconversion in disease free NHS HCWs.

Identify genetic determinants of disease severity following infection with SARS CoV-2.

3. Links to other affiliated projects

This study substantially uses existing infrastructure: Recruits into this study who are subsequently suspected to have COVID-19 can be co-recruited into ISARIC using ISARIC Ethics Ref: 13/SC/0149 (Oxford C Research Ethics Committee, UK CRN /CPMS ID 14152 IRAS ID126600 for acute samples and data collection. Sampling can be delivered via existing research personnel from furloughed projects (CLRN nurses, research fellows, Barts Bioresource). Convalescent sampling will be via an otherwise inactive Clinical Trials unit. It links to 3 additional healthy cohort multi-time point surveillance projects:

- DELPHIC COVID-19 substudy (n=1000 healthy asymptomatic in Camden via the MRC Unit for Lifelong Health and Ageing at UCL): Ethics Ref: 13/SC/0149 (Oxford C Research Ethics Committee), UK CRN /CPMS ID 14152. IRAS ID126600

- SARS-CoV-2 Acquisition in Frontline Health Care Workers– Evaluation to Inform Response (SAFER) Study– submitted to HRA. This study focuses on healthcare worker behavior, risk perception and attitudes, correlating with subclinical virology and serology (monthly) as a seroconversion endpoint, rather than early immune responses)- PI [name]/[name].

4. Methods

The proposed study is a prospective observational cohort design which will be carried out across three different trusts: Barts Health NHS Trust (St Bartholomew's Hospital, The Royal London Hospital, Whipps Cross Hospital and Newham Hospital and NHS Nightingale), Royal Free London NHS Foundation Trust (Royal Free Hospital) and University College London Hospitals NHS Foundation Trust (UCLH).

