- Asymptomatic (meaning healthy enough to attend work according to Trust policy at the time)
AND

- Work in the designated clinical environments for at least 5 hours for at least one day during the study period.

Participants will be free to withdraw from the study at any point, but collection of these data is considered to be in the public interest and will fall under the scope of a 'Public task' by the GDPR definition. Under these conditions rights to erasure and data portability do not apply, and archiving and further processing for scientific research purposes is compatible with the original purpose; no further participant data from medical records will be collected.

The research team may withdraw a participant from the study in the following situations:

- No longer meets the inclusion/exclusion criteria if participants circumstance change

b) Study period

The study period is 12 months, with baseline data collection and subsequent weekly sample and data collection for 16 weeks (until after the predicted peak of the pandemic in London). Data and samples will also be collected at 6 and 12 months (post-baseline) to monitor duration of protective immunity (i.e. decay in immunoprotection).

c) Sample Size

We have designed a primary analysis around a baseline frequency of infection of less than 0.2% average over recruitment period and a seroconversion rate of 30% of which 10% will be hospitalised and potentially enter ISARIC. However, this sample will link to other studies and the responses we are seeking are emergent and unknown. The incidence of SARS-CoV-2 among HCW (either symptomatic or asymptomatic) is not known and thus sample size calculations are challenging. The basic reproduction number (R_0) of this virus is assumed to be between 2 and 3, but one cannot estimate the number of patients admitted and the effectiveness of staff protection measures. The original sample size of $n=400$ was chosen for pragmatic reasons. The lead site (Barts) recruited 400 participants in just over 7 working days. In order to be powered to identify genetic determinants of SARS CoV-2 infection disease severity a larger cohort is required; a sample size of $n=1000$ is considered to have sufficient power for assessing for genetic influences and feasible given the rapid recruitment rates at the Barts site.

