3.4) Target blood donation in selected participants: A specific objective of the bioresource is to provide the opportunity to undertake further in depth analysis of immune responses to SARS-CoV-2 in selected participants on the basis of demographic, clinical and laboratory characteristics during the follow up period. We will invite individuals to attend an additional study visit to give one extra blood sample of up to 120 mL. This volume of blood is equivalent to one quarter of the volume donated to routine blood bank service in the UK. This volume is necessary to undertake in depth analysis of specific subsets of circulating immune cells that contribute to the immune response to the virus. Requests for participant recall by investigators will be made in writing to the bioresource steering group, who will be responsible for ensuring that the request is within the scope of the aims of the bioresource, and responsible for inviting the participants for the additional sample. Participants will be free to decline this additional sample without giving a reason and without affecting their participation in the remainder of the study.

3.5) Cardiovascular Substudy:

As the vast majority of infected participants have been pauci- or asymptomatic, this data will be important to contrast the cardiovascular effects of COVID-19 in hospitalised patients requiring simple oxygen or critical care treatment. This data will be compiled as part of the European CARTESIAN Consortium (Covid-19 effects on **ARTE**rial **Stiffness** and vascular **AgeiNg** Study). These adverse vascular effects of COVID-19 are likely to result in lasting damage to the vasculature and accelerated vascular aging. These vascular effects can be assessed using simple non-invasive tests. Identifying the presence, the causes and progression of early vascular ageing in COVID-19 patients will improve cardiovascular risk assessment and patient management. If participants agree to take part, they will undergo non-invasive measurement of pulse wave velocity, central and peripheral blood pressure (15 minutes) at the three or six and twelve months visits:

- Resting clinic brachial BP and pulse readings will be taken using a Sphygmocor device. Central blood pressure will be estimated by pulse wave analysis (PWA).
- Vascular stiffness will be assessed by carotid-femoral Pulse Wave Velocity (PWV) measurement using a Vicorder device.

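### The protocol calls n=1000 adequately powered for severity genetics without a stated basis; at its own rates (about 300 infected, 30 hospitalised) this does not hold as a general statement

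*Protocol*

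**What the plan says.** The second of the two listed aims is "to assess genetic influences on disease severity following infection with COVID-19 infection", and the matching secondary objective reads "Identify genetic determinants of disease severity following infection with SARS CoV-2" (Protocol, 2. Aims and Objectives).

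The cohort size is explained in Protocol, 4. Methods, c) Sample Size. The earlier figure of 400 is described as pragmatic. The increase is then motivated: "In order to be powered to identify genetic determinants of SARS CoV-2 infection disease severity a larger cohort is required". The same sentence goes on to say that n=1000 "is considered to have sufficient power for assessing for genetic influences" and is feasible given the recruitment speed at the lead site.

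The only rates in the document stand in the same section and belong to the primary analysis: "a seroconversion rate of 30% of which 10% will be hospitalised and potentially enter ISARIC". The section also concedes: "The incidence of SARS-CoV-2 among HCW (either symptomatic or asymptomatic) is not known and thus sample size calculations are challenging".

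Severity is not defined. The introductory text stresses "the biology of those who get non-hospitalized disease", so hospitalisation is not the only contrast in view. Section 3.5) Cardiovascular Substudy gives a glimpse of the severity mix: "As the vast majority of infected participants have been pauci- or asymptomatic".

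**The concern.** Severity after infection can be studied only in people who become infected, so the informative sample is a fraction of 1000, and the severe group a fraction of that. The power statement is nevertheless attached to the whole cohort, with none of the inputs from which power is calculated. This is not a detail that can be left to an analysis plan. The sample size section itself asserts adequacy and uses the assertion to justify 600 further participants.

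At stake is how the genetic results will be read. If the protocol says that power was sufficient, a null finding may be taken as evidence against genetic influence on severity, although moderate effects would often have been missed. The primary objective, on immune responses, is not affected.

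**Working it through.** **The plan's figure.** n=1000 cannot be reproduced as a power calculation, because no alpha, target power, effect size, allele frequency, number of variants or severity contrast is given. What can be computed is what the protocol's rates would deliver.

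**Inputs from the protocol** (c) Sample Size): n = 1000, previously 400; seroconversion 30%; 10% of those hospitalised.

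- n = 1000: 1000 × 0.30 = 300 infected; 300 × 0.10 = 30 hospitalised, 270 not.
- n = 400: 400 × 0.30 = 120 infected; 120 × 0.10 = 12 hospitalised, 108 not.

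**Assumed inputs** (not in the protocol): additive test, Hardy-Weinberg proportions, allele frequency f of 0.3 or 0.1 in the less severe group, two-sided alpha 0.05 for one variant or 0.05/20 = 0.0025 for 20 variants (Bonferroni), target power 80%, no dropout. Only the 30 vs 270 split follows from the protocol's rates; 60 vs 240 and 150 vs 150 are assumed alternatives.

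**Formula** (allelic two-proportion approximation, two alleles per person). The allele frequency in the severe group is p1 = OR·f / (1 − f + OR·f). With N1 and N0 alleles in the two groups and pooled frequency p̄:

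- SE0 = √[p̄(1 − p̄)(1/N1 + 1/N0)]
- SE1 = √[p1(1 − p1)/N1 + f(1 − f)/N0]
- power ≈ Φ[(p1 − f − z·SE0)/SE1]

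**Worked case**, 30 vs 270, f = 0.3, OR 2.0, alpha 0.05 (z = 1.96):

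- p1 = 0.6/1.3 = 0.4615; N1 = 60; N0 = 540; p̄ = (60 × 0.4615 + 540 × 0.3)/600 = 0.3162
- SE0 = 0.0633; SE1 = 0.0673
- power = Φ[(0.1615 − 1.96 × 0.0633)/0.0673] = Φ(0.56) = 71%

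With f = 0.1: p1 = 0.1818, p̄ = 0.1082, SE0 = 0.0423, SE1 = 0.0514, and power = Φ(−0.02) = 49%. Simulation of the trend test (200,000 data sets per cell) gives 70.8% and 48.1%, so the two methods agree.

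**Simulated results for 300 infected** (each pair is f = 0.3, then f = 0.1):

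| Split | Detectable OR, 1 variant | Detectable OR, 20 variants | Power at OR 2.0, 1 variant | Power at OR 2.0, 20 variants |
|---|---|---|---|---|
| 30 vs 270 (protocol rates) | 2.2, 2.7 | 2.9, 3.6 | 71%, 48% | 32%, 18% |
| 60 vs 240 (assumed) | 1.8, 2.2 | 2.2, 2.8 | 91%, 68% | 62%, 32% |
| 150 vs 150 (assumed) | 1.6, 2.0 | 1.9, 2.5 | 98%, 83% | 85%, 44% |

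**Sensitivity.**

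- *Graded outcome.* Three ordered categories in the 300 infected (assumed 45/45/10%, proportional odds, allele frequency defined in all infected) give 98% and 75% power at OR 2.0, and 65% and 34% at OR 1.5, one variant.
- *Infection rate.* At an assumed 40% seroconversion with 10% severe, OR 2.0 has 82% and 58% power for one variant. At an assumed 20%, the value for f = 0.3 is 54%.
- *Effect of the enlargement.* At n = 400 (12 vs 108) the detectable OR for one variant would be 3.3 and 4.2, against 2.2 and 2.7 at n = 1000.
- *Other reading of the 10%.* If it meant 10 of the 30 percentage points, the split would be 100 vs 200. The formula above then gives a detectable OR of about 1.7 and 2.0 for one variant.

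**The case against.** The strongest reply is that nothing in the protocol has been refuted. It states no genetic effect size or alpha that could be wrong. Nearly every input to the power figures above is assumed, and at OR 2.0 for one variant the power runs from 48% to 98% depending on split and allele frequency. The rates are attached to the primary analysis, and incidence is called unknown. Severity is undefined, and the study records graded information such as symptoms, days away from work and treatment, so a more even or ordered contrast is plausible. The study is also a bioresource: processing and analysis of the blood samples are placed outside the fieldwork application, samples are meant to be shared nationally, and linkage and expansion are foreseen.

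Much of this stands. It shows that the power figures are illustrations, and that some analyses would be well powered. It does not supply a basis for the statement. An unknown incidence argues against asserting sufficient power, not for it. Linkage and expansion are not quantified, and the assertion is made for n=1000. The remark that most infected participants had few or no symptoms suggests a small group with marked illness, although it does not settle how the pauci-symptomatic and asymptomatic would divide.

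A reader might go further and infer that n=1000 is the wrong size, that every genetic analysis is underpowered, or that the objective should be relabelled exploratory with the cohort size resting mainly on feasibility. The documents do not support any of these. With a 150 vs 150 contrast, OR 2.0 has 83% to 98% power for one variant, and the enlargement clearly lowers the detectable effect.

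**Conclusion.** The point holds in a limited form. The statement of sufficient power has no stated basis and does not hold as a general statement at the plan's own rates. For the one contrast that those rates define, 30 hospitalised vs 270 other infected, 80% power needs a per-allele OR of about 2.2 to 2.7 for a single variant, and about 2.9 to 3.6 with 20 variants. It can hold for large effects in one or a few variants, for somewhat smaller effects with a more even or graded severity contrast, or at a higher infection rate.

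The counts of 300 and 30 follow directly from the protocol. The detectable ORs rest on the assumed alpha, allele frequencies, additive model and complete follow-up. Confidence is high that the basis is missing; the exact power depends on choices that the protocol does not state. The statement should be corrected, since it carries the justification for the enlargement, but it concerns a secondary objective and leaves the primary one untouched.

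**What to change.** In c) Sample Size, replace the sufficiency wording with:

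1. the expected counts at the assumed rates, about 300 infected and about 30 hospitalised;
2. the per-allele OR detectable with 80% power for the intended severity contrast, with alpha, allele frequency and number of variants given explicitly as assumptions;
3. a sentence saying that smaller effects may be missed.

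This changes wording only: no new participants, visits or samples. The cost is a less favourable power statement for a secondary objective, and the need to name the severity contrast intended. The status of the objective and the target of 1000 can stay as they are.

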We anticipate using multiple sites to secure staff participation to 1000, subject to local site approval. Should it be possible with sufficient interest, staff and consumables, this number will be expanded. Furthermore, if there is sufficient interest in study participation, recruitment will be stratified by sampling by sex, age and ethnicity. Currently age categories proposed are between 25-40, >40-55, >55.

d) Study design

A baseline questionnaire and sample collection will be performed, followed by weekly resampling (Figure 1) for 16 weeks, and two additional visits at 6 and 12 months time.

1 Baseline questionnaire

Consented study participants will complete a brief baseline questionnaire which collects standard variables related to demographics (including household size and details), anthropometry, past medical history including drug and vaccination history and SARS-CoV-2 symptoms, exposure and prior testing, and contact history including details of work-based exposure and personal protective equipment used. See Appendix 4 (RedCap eCRF) for details.

2 Baseline sample collection

We aim to capture pre-infection levels of several markers (and how they evolve), including but not restricted to immune cell population (e.g., pre-infection antibody levels against other coronaviruses might influence host response to SARS-CoV-2), genomic and transcriptomic profiles. Sample collection will include:

a. Nose swabs: Nose swabs will be performed at baseline and weekly for the duration of the study. Participants will self-swab to minimise the risk of potential contamination or aerosolisation. Swab samples will be collected from a designated collection point by the research staff and submitted to the designated laboratory at each site within 48 hours of collection. Only staff who are asymptomatic and not currently self-isolating at home will be recruited for baseline sample collection.

b. Blood samples (summarized in Table 1):

- Blood samples collected at baseline will consist of 1 x blue PAXgene RNA (2.5ml), 2 x yellow biochemistry gel tube (6ml), 2 purple EDTA plasma (5ml) and 1 purple EDTA DNA (5ml) totalling 29.5mL. Research staff will arrange blood sample collection in the hospital at a conveniently accessible location and at a suitable time for the participant. Blood samples will be stored at -20, 40 or 80°F for the first week until delivery to secure -80C. Processing, aliquoting and analysis will be handled outside this fieldwork application.

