Saliva sample [Week 4, convalescent, 2x at months 6 and 12]	Freeze -80°C	Molecular testing for SARS-CoV-2 ± other pathogens
Serum tube [Baseline, all follow ups, convalescent]	Analyse	SARS-CoV-2 antibody testing i.e. IgG, IgM

PAX RNA gene tube [Baseline, all follow ups, convalescent]	Freeze -80°C	Transcriptomics
PAX DNA gene tube [Baseline only]	Freeze -80°C	Genetics

F/U = follow-up. Other abbreviations see main text.

3.2) Symptomatic course or suspected (not-confirmed) SARS-CoV-2 infection

necessitating self-isolation at home– we will record the number of days participants remain away from work, any treatment received, and whether they receive a formal SARS-CoV-2 diagnosis as the result of routine clinical testing. During their illness, they will be advised to follow Public Health England national guidance and will be assessed and treated by routine clinical services, as required. We will offer the participants to opt-in to have a swab and saliva collection tube sent to their home address for self-sampling.

On the first return after a symptomatic course of suspected (not-confirmed) SARS-CoV-2 infection necessitating self-isolation at home, they rejoin the sampling scheme as detailed in 3.1. On this visit we will take an additional 11mL blood (1 x biochemistry; 1 x EDTA for PBMCs = total 19.5mL) and a saliva sample.

3.3) SARS-CoV-2 positive participants admitted to hospital– participants with a confirmed SARS-CoV-2 positivity diagnosis (on the basis of research or clinically mediated testing) will be asked to report this to the study team. At the point of hospital admission, such participants automatically enter the ISARIC trial for subsequent sample collection and analysis.

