Safety measures related to staff, research team members, recruited participants are detailed in section 6 (“Duty of care”).

4 Sample and data collection

After sample collection all vials/tubes will be consolidated in a transport bag. Only the EDTA tube for PBMCs (peripheral blood mononuclear cells) will be spun (by [name], QMUL) to reduce the risk to staff processing samples. All other tubes and nasal swabs will be frozen in the same gel separator tube used for sample collection immediately at -80 degrees on site. Table 2 details the sampling strategy.

Data collection instruments are in RedCap and based on those of ISARIC. Specific questions related to immune status and home/work exposure are included in the eCRF. (appendix 4).

5 Biosample procedures (as per Trust policy and PPE guidance)

Obtaining baseline nasal swab samples

- Wear designated aprons, surgical masks and visors.
- Apply alcohol gel to hands and then apply fresh gloves.
- Explain procedure clearly to HCW.
- Label the sample tube with the appropriate participant number.
- Ask participants to open their mouths and say “ahhh”.
- Swab nostril and/or posterior pharynx (for the latter avoid saliva and tongue, rotating swab covering left and right faucial pillars).
- Place COPAN swab immediately into a sterile tube containing 2-3 ml of viral transport media.
- Follow the instructions in section below for transport of samples.

Obtaining baseline blood samples

- No sharp should be exposed/unsheathed without the necessary sharps container available in which to discard it.
- Label the blood tube with the appropriate participant number.
- Identify the vein and clean the overlying skin with a chlorhexidine skin swab. Discard in a clinical waste bag.
- Using the BD vacutainer push button blood collection set with pre-attached holder, insert needle into identified vein. Then attach to the vacutainer system:
 - o 5ml yellow topped serum blood collection tube x 2
 - o 5ml purple topped EDTA blood collection tube x 2
 - o 2.5ml PAXgeneRNA blood collection tube
- Once the blood tubes are full, remove the tube from the collection system, place in 2 leak proof bags with absorbent material (Safety gel granules) and seal.
 - Press the push button on the blood collection system and the needle will retract from the vein into the plastic receptacle, ensuring a completely sharp safe system.
 - Discard the used blood collection system into the sharps container.

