Usually for a study like this, all participants will receive clinical advice on managing any symptoms through the Chief Investigator as well as any clinically actionable results from FBC, U&E, CRP. Here however, with a rapidly evolving situation, recruited staff will use the same advice channels as all other staff in line with NHS/ Public Health England recommendations.

e) Safety: Potential Harm and Risks

Study participants: This is a study recruiting HCW who are well and attending work. They are therefore self-declaring as asymptomatic, and are attending a “dirty” healthcare environment. Swabs are the standard COPAN nasal flu swabs and are not considered a coughing risk with training. Blood sample collection may cause slight bruising at the venepuncture site, but weekly sampling is not an unusual sampling periodicity. The total blood volume at baseline is estimated at ~30mL. As with all staff recruitment projects, there is concern about coercion to enrol. To mitigate against this we are following the Barts “Guidance on obtaining and using human blood and tissue from healthy volunteers for research purposes”.

Research staff: At enrolment study participants will consist of well and asymptomatic HCWs attending work, but during subsequent follow-up HCWs may well develop symptoms or a formal SARS-CoV-2 diagnosis. No participants should be attending if symptomatic as they should not be working. Protection of research staff collecting samples will consist of surgical masks, visor, gloves and apron implying minimal consumption of PPE as the visor and surgical mask can be reused by one nurse for multiple encounters whilst gloves will be changed each time. This will be as per Trust policy. Staff will train participants to obtain their own nasal swabs to minimise the risk of staff exposure and maximise yield. Saliva collection is via commercially-available kits to minimise potential for spillage.

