Appendix 5. Biosample procedures

1. Obtaining nasal swab samples

- Apply alcohol gel to hands and then apply fresh gloves.
- Explain procedure clearly to participants and explain that they will be collecting their own swabs and need to swab each nostril for 15 seconds etc.
- Label the sample tube with the appropriate participant number.
- Ask the participants to collect their own samples
- Place COPAN swabs immediately into sterile tubes containing 2-3 ml of viral transport media.
- Then follow the instructions in the section below for transport of samples.

2. Obtaining blood samples

- NO sharp should be exposed/unsheathed without the necessary sharps container available in which to discard it.
- Label the blood tube with the appropriate participant number.
- Identify the vein and clean the overlying skin with a chlorhexidine skin swab. Discard in a clinical waste bag.
- Using the BD vacutainer push button blood collection set with pre-attached holder, insert needle into identified vein. Then attach to the vacutainer system and collect the blood bottles outlined in Table 1
- Once the blood tubes are full, remove the tube from the collection system, place in 2 leak proof bags with absorbent material (Safety gel granules) and seal.
- Press the push button on the blood collection system and the needle will retract from the vein into the plastic receptacle, ensuring a completely sharp safe system.
- Discard the used blood collection system into the sharps container.
- Discard any gauze used to stop bleeding into the clinical waste bag.
- Follow the instructions in the section below for containment of samples for transport.

3. Obtain saliva sample: collection kit including OmniGene 505 collection tube; a biohazard bag.

Donation should typically take less than 5 minutes:

- I. Do NOT remove the plastic film from the funnel lid.
- II. Allow saliva to pool under the tongue.

- III. With the head tilted forwards, gently guide saliva from the mouth into the collection tube. This way, a clear, non-foaming liquid is produced.
- IV. Spit into funnel until the amount of liquid (not bubbles) reaches the fill line shown in the picture below.
- V. Do not close the funnel lid. Hold the tube upright. Unscrew the funnel from the tube.
- VI. Use the small cap to close the tube tightly. Discard the funnel.
- VII. Place the tube into the biohazard bag and seal it closed. Place the biohazard bag into the fridge until collection.

4. Post-sampling

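### The bench procedure for the baseline blood draw lists five tubes (22.5 mL) and no DNA tube, where section d)2b and Table 1 schedule six (29.5 mL), one of them a baseline-only DNA tube

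*Protocol*

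**What the plan says.** The baseline draw is described in several places in the protocol.

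- **Methods d)2b** itemises one 2.5 mL RNA tube, two 6 mL serum tubes, and "2 purple EDTA plasma (5ml) and 1 purple EDTA DNA (5ml) totalling 29.5mL".
- **Table 1** has the same tubes and the same total in its baseline column. It schedules the DNA tube once at baseline and at no later visit.
- **Methods d)5**, in the needle procedure for baseline blood, gives a separate list: "5ml yellow topped serum blood collection tube x 2", "5ml purple topped EDTA blood collection tube x 2" and one 2.5 mL RNA tube. It does not mention a DNA tube and does not refer to Table 1.
- **Appendix 5, step 2**, a parallel bench procedure, tells staff to "collect the blood bottles outlined in Table 1".
- **Section e) Safety** says: "The total blood volume at baseline is estimated at ~30mL".
- **Methods d)4**, just before d)5, says "Table 2 details the sampling strategy". Table 2 lists a "PAX DNA gene tube [Baseline only" time point for genetics, so it too expects a DNA sample at baseline. It names a PAX tube, however, where d)2b and Table 1 have a purple EDTA tube.

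**The concern.** Two bench procedures for one visit, d)5 and Appendix 5, lead to different sets of tubes, and the protocol does not say which takes precedence. Staff working from d)5 would comply with that section and still miss one tube that d)2b and Table 1 schedule.

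What is lost depends on which tube is missing. If it is the DNA tube, no later visit in Table 1 schedules another. Genetic determinants of severity are a secondary objective, and section c) gives the genetic analysis as the reason for going from 400 to 1000 participants. If it is a plasma/PBMC tube, the baseline immune sample is one tube short, and baseline immune responses are part of the primary objective.

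Nothing near d)5 settles the matter. Neither EDTA tube in d)5 is labelled by purpose. Section d)4 says "Only the EDTA tube for PBMCs (peripheral blood mononuclear cells) will be spun", which identifies one tube and leaves the other open. A reader who checks d)5 against Table 2 for a DNA tube is looking for a PAX tube and finds none.

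**Working it through.** **Reproducing the plan's own total.**

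d)2b: 1 × 2.5 (RNA) + 2 × 6 (serum) + 2 × 5 (EDTA plasma) + 1 × 5 (EDTA DNA) = 2.5 + 12 + 10 + 5 = 29.5 mL, 6 tubes.

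Table 1, baseline column: 1 × 5 (DNA) + 2 × 5 (PBMC/plasma) + 1 × 2.5 (RNA) + 2 × 6 (serum) = 29.5 mL, 6 tubes.

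Both agree with the stated 29.5 mL and with the rounded figure in section e).

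**The d)5 list.**

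2 × 5 (serum) + 2 × 5 (EDTA) + 1 × 2.5 (RNA) = 22.5 mL, 5 tubes.

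**Splitting the gap.** 29.5 − 22.5 = 7.0 mL.

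| Tube | d)2b and Table 1 | d)5 | Difference |
|---|---|---|---|
| EDTA | 3 × 5 = 15 mL | 2 × 5 = 10 mL | 5 mL (one tube) |
| Serum | 2 × 6 = 12 mL | 2 × 5 = 10 mL | 2 mL (tube size) |
| RNA | 1 × 2.5 mL | 1 × 2.5 mL | 0 |

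Adding a third EDTA tube to d)5 gives 22.5 + 5 = 27.5 mL. Making the serum tubes 6 mL adds 2 mL and gives 29.5 mL. These two differences explain the whole gap. Because the tube count differs, rounding cannot account for it.

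**What a participant bled to d)5 would have.**

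- If the undrawn tube is DNA: 0 of 1 DNA tubes and 2 of 2 plasma/PBMC tubes.
- If it is plasma/PBMC: 1 of 1 DNA tubes and 1 of 2 plasma/PBMC tubes.

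**Whether later visits make it good.** After baseline, the scheduled visits in Table 1 have 4 × 1 (weeks 4, 8, 12, 16) + 2 × 7 (months 6 and 12) = 18 PBMC/plasma EDTA tubes and 0 DNA tubes. Those tubes might yield DNA, but the protocol assigns none of them to genetics. The re-bleed provision in d)2b covers sample failure. Its examples are partial loss of vacuum, partial venous access and failed processing, and a tube that was never drawn is not among them.

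**The case against.** The strongest reply is that the protocol as a whole points to the fuller draw. Section d)2b itemises it, Table 1 repeats it, section e) gives a matching volume, Appendix 5 sends staff to Table 1, and Table 2 lists a baseline DNA tube. Section d)4 even directs the reader to Table 2 immediately before d)5. Most of d)5 concerns protective equipment, sharps, labelling and waste, and the sampling schedule is set elsewhere. On this view d)5 is a handling text whose tube list was not reconciled with the schedule, and few or no participants were bled to it.

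Most of this stands, and it limits the weight of the point. It does not remove the contradiction, because d)5 is a baseline-specific procedure with its own explicit list.

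A reader might go further and infer that the DNA tube is the one omitted, or that the genetic objective is lost. The documents support neither inference. Section d)5 does not say which EDTA tube is left out, nothing shows how many participants were bled to it, and later EDTA blood might yield DNA. Nor is this a fault of design: a DNA tube at baseline is stated consistently in d)2b, Table 1 and Table 2 apart from its name.

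**Conclusion.** The inconsistency holds and is minor. Per participant bled to d)5, the draw is 22.5 mL instead of 29.5 mL, with 2 of 3 EDTA tubes and 10 of 12 mL of serum. One scheduled EDTA tube is missing, and it could be the baseline-only DNA tube or a plasma/PBMC tube.

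The consequence rests on one assumption, that some staff worked from the d)5 list and not from Table 1. The protocol gives no count. The number could in principle lie anywhere from none to all enrolled, and it may be near zero given how many other sections support the fuller draw. No study-level loss is claimed.

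**What to change.** - In d)5, replace only the tube list with the instruction already used in Appendix 5, to "collect the blood bottles outlined in Table 1". This settles both the EDTA count and the serum tube size.
- In Table 2, reconcile the DNA tube's name with the purple EDTA DNA tube in d)2b and Table 1.
- Check the existing sample log for participants without a baseline DNA tube. This also shows whether anyone was affected.
- The sponsor should state whether the re-bleed provision in d)2b extends to a tube that was never drawn.
- As a minor matter, reconcile the d)5 swab lines with the rest of the protocol. They read as if staff take the swab and allow a throat site, whereas d)2a, section e) and Appendix 5 describe a nasal self-swab. Change only the lines on site and operator. The opening d)5 line on aprons, masks and visors should stay, because Appendix 5 step 1 has no equivalent.

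The cost is a few wording changes and one log check. No visit or tube is added to the schedule.
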